4/10/19	Title Page	Study coordinator name and contact info changed.
4/10/19	7.1.3	Clarification on AE's that are to be reported in the database.
5/8/20	Title Page, 7.3.1	PI changed from [name] to [name], additional study staff updated

STUDY SCHEMA

X

PROTOCOL SUMMARY

Protocol Number/Title	CASE4318 Feasibility Study of Temporally Feathered Radiation Therapy (TFRT) for Head and Neck Squamous Cell Carcinoma: Means of Toxicity Reduction
Study Phase	Feasibility
Brief Background/Rationale	
Intensity-modulated radiation therapy (IMRT) has allowed for optimization of three-dimensional spatial radiation dose distributions permitting target coverage while reducing normal tissue toxicity. However, acute and late radiation-induced normal tissue toxicity is a major contributor to patients' quality of life and often a dose-limiting factor in the definitive treatment of cancer with radiation therapy. We propose the next logical step in the evolution of IMRT incorporates canonical radiobiological principles, optimizing the temporal dimension through which radiation therapy is delivered to further reduce radiation-induced toxicity by increased time for normal tissue recovery. This new technique of radiation planning and delivery is termed Temporally Feathered Radiation Therapy (TFRT). TFRT has been previously modeled in silico and has demonstrated potential to reduce normal tissue toxicity. Given that TFRT is dependent on normal tissue recovery, a dynamic normal tissue complication probability (NTCP) model is used to ascertain the potential benefits of TFRT as compared to conventional IMRT planning. In this study, we will examine the feasibility of generating and delivering TFRT plans in the modern clinical workflow. Importantly, the radiation dose to the target volume is not altered and therefore this technique of radiation planning only examines techniques to reduce toxicity. All radiation prescription doses used in this study are determined as per current standards of care.

Primary Objective	
Primary Endpoints
 
Feasibility of TFRT planning and delivery defined as patient starting radiation within 15 days of CT simulation.

Secondary Objective(s)	
Secondary Endpoints
 
 (1) Estimate acute grade 3-5 toxicity (within 90 days after RT) (2) Patient-reported outcomes of toxicity during and after TFRT. (3) Compliance with plan delivery
Exploratory Objective(s)	
Exploratory Endpoints (s)
 
 • Compare doses to organs at risk delivered by TFRT compared to conventional IMRT plans on a per patient basis

Correlative Objective(s)	Correlative Endpoint(s) N/A
Sample Size	5 patients Patients age >18 years, male and female
Disease sites/Conditions with ICD 10 codes	C01 Base of Tongue C05 Palate (soft) C09 Tonsil C10 Oropharynx C10 Epiglottis C11 Nasopharynx C11 Pharyngeal Wall C12-C13 Hypopharynx C13 AE Fold C14 Pharynx (NOS) C32 True Vocal Cord C32 Glottis C32 Larynx C32 Supraglottic C44 Squamous Cell Cancer
Interventions	Temporally Feathered Radiation Therapy (TFRT)

ABBREVIATIONS

CCCC	Case Comprehensive Cancer Center
CRF	Case Report Form
DCRU	Dahm's Clinical Research Unit
DSTC	Data Safety and Toxicity Committee
ICF	Informed Consent Form
IRB	Institutional Review Board
PRMC	Protocol Review and Monitoring Committee
SOC	Standard of Care
CCF	Cleveland Clinic Foundation
UH	University Hospitals
TFRT	Temporally Feathered Radiation Therapy
IMRT	Intensity Modulated Radiation Therapy
OAR	Organ At Risk
d_s	Standard fractional dose
d_L	Low fractional dose
d_H	High fractional dose
NTCP	Normal tissue complication probability

TABLE OF CONTENTS

1.0 Introduction

1.1 Background of Study Disease

In 2017, the incidence of new cases of head and malignancies, including the oral cavity and pharynx was estimated to be about 1.7 million with about 600,000 deaths worldwide.¹ These cancers have been historically treated with a surgical approach; however given the morbidity of surgery, the standard has shifted to definitive non-surgical organ sparing approaches including radiotherapy with or without concurrent chemotherapy.² Conventional techniques of radiotherapy and chemotherapy resulted in high rates of late effects, such as dysphagia, radionecrosis, and xerostomia. With the advancement of radiotherapy techniques through the years, specifically the adoption of intensity-modulated radiotherapy (IMRT) coupled with image guidance, the practitioner now has greater control over the physical distribution of dose over the target volume and nearby surrounding structures. This has led to decreased late toxicity rates. In a recent study of patients receiving definitive radiotherapy with or without chemotherapy for HPV-related oropharynx cancer, the cumulative incidence of severe late toxicity at 2-years after completing treatment was 2.3%, whereas 42% of patients experienced grade 3 or higher acute toxicity.² The most common grade 3 or greater acute toxicity was dysphagia (24%), followed by mucositis (17%), and dermatitis (8%). For those who required feeding tube placement, the median duration of acute feeding tube use was 1.7 months. Of the patients followed greater than one year without local failure, 24% experienced grade 2 xerostomia. Notably, in historic trials, higher rates of toxicity have also been recorded with concurrent chemotherapy and radiotherapy.³⁻⁷ Quality of life also declines following therapy. Though most patients recover global quality of life by 12 months, deterioration in physical functioning, fatigue, xerostomia, and sticky saliva persist beyond 12 months in head and neck cancer survivors.^{8,9} In this study we aim to further decrease acute and late toxicities associated with radiotherapy. We examine a new technique termed temporally feathered radiation therapy (TFRT), through which the dose delivered to the target volume remains unchanged while the fractional dose delivered to the surrounding organs at risk is altered.

The biologic basis of dose and fractionation arises from the four pillars of radiobiology: (i) repair of sub-lethal damage, (ii) reassortment of cells within the cell cycle, (iii) repopulation, and (iv) reoxygenation.¹⁰ Recovery from radiation-induced toxicity is primarily dependent on sub-lethal damage repair and repopulation. For this reason, fractionated radiotherapy still predominates in the clinic. As a low fractional dose of radiation is delivered daily, consistent insult is delivered to tumor cells while allowing time for normal tissue recovery between fractions. Despite this, as discussed above, toxicity still manifests mid-way or toward the end of most treatment courses acutely and late toxicities remain dose-limiting. Attention has been turned to techniques to widen the therapeutic ratio between tumor control probability (TCP) and normal tissue complication probability (NTCP). This had been achieved previously by pharmaceuticals such as radiosensitizers and radioprotectants, until the advent of intensity modulated radiation therapy (IMRT), which now is one of the greatest contributors to reduced toxicity associated with radiotherapy.^{2,11,12} The implementation of IMRT into clinical practice

took nearly 50 years from when [name] solved the inverse problem of IMRT in the 1940s, until [name] illustrated the IMRT principles in 1988, and ultimately when the Peacock planning system was used to treat the first patient with IMRT in the mid-1990s.¹³⁻¹⁷

As an extension of IMRT, other researchers namely [name] have examined the role of altering both the fractional dose delivered to the target as well as the organs at risk to continue to widen the therapeutic ratio.¹⁸⁻²² Temporally feathered radiation therapy takes a different approach to reducing toxicity, without altering target volume coverage or dosing. Temporally feathered radiation therapy optimizes not only the physical distributions of dose, but also the time through which radiation therapy is delivered with the goal of allowing increased time for normal tissue recovery between fractional doses. Preclinical data demonstrating the potential benefit of TFRT are discussed below (section 1.2.1).²³

1.2 Temporally Feathered Radiation Therapy

1.2.1 Preclinical Data

Temporally feathered radiation therapy is designed for targets within close proximity to multiple organs at risk. The foundation of this planning technique is the rotation of radiation dose to the nearby organs at risk on a daily basis, and hence the term “feathering”. Radiation dose feathering is a technique that has been long used for creating a uniform distribution of dose across radiation field junctions at which hot or cold spots may occur. In TFRT planning, the physical dose is deliberately feathered among the neighboring organs at risk unevenly. Temporally feathered radiation plans are composed of 5 isocurative *subplans* which are scheduled to be delivered once per week as illustrated in Figure 1. Each of these subplans delivers a therapeutic dose of radiation therapy to the target, however one organ at risk is chosen to be deprioritized per subplan and therefore receive a slightly higher fractional dose (d_H) as compared to the standard fractional dose (d_S) delivered by conventional planning. d_H is defined as a measure of dose distributed over a deprioritized organ. The following is true: $d_H > d_S > d_L$. Resultantly, each OAR which received a slightly higher fractional dose once weekly, followed by slightly lower fractional dose the remaining four fractions of that week as reflected in the other four subplans. The hypothesis is that if d_H is delivered to an organ at risk once weekly followed by four d_L (lower fractional dose), there is increased time for normal tissue recovery.

[figure not shown]

Figure 1. Schematic representation of Temporally Feathered Radiation Therapy.

The target volume (*black pentagon*) is surrounded by 5 organs at risk (*circles*). Five individual radiation plans are created for each day of the week whereby a higher fractional dose, d_H , is delivered to the OAR of interest (*grey*) and the remaining four OARs receive a lower fractional dose, d_L .

In silico simulations, TFRT demonstrated potential for reduced normal tissue toxicity compared to conventionally planned IMRT as demonstrated in Figure 2.²³ The sequencing of high and low fractional doses delivered to OARs by TFRT plans suggested increased normal tissue recovery, and hence less overall radiation-induced toxicity compared to conventionally planned IMRT. The simulations were conducted using the following dynamic normal tissue complication probability model (equation 1) which accounts for normal tissue recovery in response to radiation therapy.²³

$$\frac{dN}{dt} = \mu N(t)(1 - N(t)) - \delta(t_i) RT(d) N(t)(1 - N(t)), \quad (1)$$

The organ-specific parameter $\mu > 0$ represents the recovery rate of radiation-induced damage. $N(t) < N(0)$ represents the level of normal tissue damage by radiotherapy, considering that normal tissue at homeostasis with a 1% turnover rate would be denoted as $N(0) = 0.99$. Small values of $N(t)$ relate to severe damage. The effect of radiation is included by the loss term $\delta(t_i) RT(d) N(t)(1 - N(t))$ where $\delta(t_i)$ is a characteristic function equal to 1 at the time of irradiation t_i , and zero in other case. The magnitude of toxicity reduction by TFRT planning was found to depend on corresponding standard fractional dose of IMRT and organ-specific recovery rate of sub-lethal radiation-induced damage.

[figure not shown]

Figure 2. Comparison of conventionally fractionated IMRT and TFRT with respect to the standard fractional dose (d_s) and organ-specific recovery rate (μ). (a) Overall potential benefit (OPB_{TF}) and (b) maximum potential benefit (MAX_{TF}) of TFRT over conventional planned IMRT. (I-III) Top panels represent the single cases marked by stars in (a). The x- and y-axes represent $\Delta L = d_s - d_L$ and $\Delta H = d_H - d_s$, respectively. Bottom panels show time-evolution of OAR toxicity included by the IMRT and TFRT plans corresponding to the location marked by diamonds in the top panels.

Further dosimetric evaluations were conducted with IMRT head and neck cases that were replanned with TFRT technique. As illustrated in figure 3, the TFRT plans were achievable while maintaining the dose delivered to the planning target volume.

[figure not shown]

Figure 3. Proof of principle of Temporally Feathered Radiation Therapy. Panel A illustrates changes in OAR toxicity and NTCP over time for varying OAR recovery rates. Panel B demonstrates a dose volume histogram for the target in a TFRT plan (red) compared to conventionally planned IMRT (black). Panel C demonstrates axial images of a head and neck plan with superimposed isodose lines for conventionally planned IMRT, a TFRT plan with d_H delivered to the OAR, and a TFRT plan with d_L delivered to the OAR (left to right).

1.2.2 Clinical Data

There are no available clinical research data to date on temporally feathered radiation therapy.

1.3 Rationale

Given prior preclinical data suggesting the potential for reduced normal tissue toxicity with TFRT, we will now evaluate the feasibility of treatment planning and delivery in current clinical workflow. Subsequent studies will be powered for toxicity outcomes. Patients with head and neck malignancies were chosen, as the current standard of care requires conventionally fractionated radiation therapy over 7 weeks. Due to the anatomy

of the region, the target volume often is surrounded by multiple organs at risk. Therefore, head and neck malignancies are a prime example in which temporally feathered radiation therapy may decrease normal tissue toxicity.

2.0 Objectives

2.1 Primary Objective

To determine feasibility of TFRT planning and delivery for head and neck squamous cell carcinoma defined as patient starting radiation within 15 days of simulation.

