3.0 Study Design

3.1 Study design including dose escalation / cohorts

This study is planned as a single arm feasibility trial to demonstrate clinical delivery of TFRT plans. Five patients will be accrued as a single cohort.

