3.2 Number of Subjects

Five patients will be enrolled in this trial.

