6.2 Dose Specifications

6.2.1 Dose Fractionation

Patients must be eligible to receive 70 Gy in 35 fractions to the primary target (PTV_7000) and to receive 56 Gy in 35 fractions to the elective volume (PTV_5600). The doses are prescribed at the edge of the PTV. Treatment will be delivered once daily from Monday to Friday over 7 weeks. Missed treatments can be compensated for by treating on the Saturday or Sunday of that week, or adding to the end of treatment.

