11.0 STATISTICAL CONSIDERATIONS

This study is designed as a feasibility study, with the goal of accruing 5 patients over the course of one year from trial opening. The primary objective is to determine the feasibility of TFRT planning and delivery in a modern clinical workflow. Feasibility is defined as a patient starting radiotherapy within 15 days of simulation. The TFRT technique will be deemed feasible if 3/5 patients meet the above criteria.

Descriptive statistics will be applied. Secondary endpoints include estimates of (1) acute grade 3-5 toxicity as per CTCAE version 4, (2) estimates of patient-reported outcomes during and after TFRT delivery using EORTC QLQ-H&N35, EORTC QLQ-C30, and Xerostomia Questionnaire (XO) and (3) compliance with plan delivery.

The patient-reported outcomes (PROs) from the above questionnaires will be collected at week 1 (baseline), week 4, and week 7 of treatment, as well as 2 weeks, 4 weeks, and 3 months post completion of treatment radiation. Descriptive associations between PROs and CTCAE toxicity criteria will be reported.

REFERENCES

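### The primary objective claims feasibility of TFRT planning and delivery, but the 3/5 rule tests only an on-time start and cannot speak to delivery beyond the first fraction

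*Combined protocol and SAP*

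**What the plan says.** The protocol summary gives the primary endpoint as "Feasibility of TFRT planning and delivery defined as patient starting radiation within 15 days of CT simulation". Section 2.1 words the objective as "To determine feasibility of TFRT planning and delivery", with feasibility "defined as patient starting radiation within 15 days of simulation". Section 3.1 describes a "single arm feasibility trial to demonstrate clinical delivery of TFRT plans". Section 11.0 again names planning and delivery as the primary objective, then says "Feasibility is defined as a patient starting radiotherapy within 15 days of simulation" and adds the decision rule: "The TFRT technique will be deemed feasible if 3/5 patients meet the above criteria". Section 3.2 fixes the sample size at five.

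The course to be delivered is long. Section 6.2.1 gives 35 fractions and says "Treatment will be delivered once daily from Monday to Friday over 7 weeks". Section 1.2.1 describes five subplans, each given once a week, and Appendix II fixes their order as A to E.

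Delivery after the start appears in the objectives only as secondary endpoint 3, compliance with plan delivery (summary, 2.2 and 11.0). It has no patient-level definition, is summarised descriptively and does not enter the 3/5 rule. Section 6.6.3 sends a patient who cannot start TFRT within 15 days to a standard IMRT plan prepared in advance.

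**The concern.** The stated question has two parts, planning and delivery, and the criterion is settled when the first fraction is given. TFRT is defined by the rotation of subplans across the week, so one fraction gives one of the five subplans and no rotation has yet taken place. What follows is the part of delivery that differs from ordinary IMRT: selecting the correct subplan each day, keeping the order after missed fractions, and continuing for seven weeks. None of it can change the primary conclusion.

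The wording adds a second gap. The criterion refers to starting radiation or radiotherapy, not to starting the TFRT plan. Because a fallback IMRT plan exists, the two are not the same event.

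The headline conclusion is at stake. Section 1.2.2 reports no clinical data on TFRT, and section 1.3 expects later studies powered for toxicity. A statement that the technique is feasible would naturally be read by those planning them as covering delivery of the feathered course.

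**Working it through.** **1. What the plan states.** The decision rule is 3 of 5. No target rate, null rate, alpha or power is given, so there is no operating figure to reproduce.

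**2. The passages side by side.**

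| Place | What is claimed | Criterion attached |
|---|---|---|
| Summary, primary endpoint | planning and delivery | start within 15 days of CT simulation |
| 2.1 | planning and delivery | start within 15 days of simulation |
| 3.1 | clinical delivery of TFRT plans | none |
| 11.0 | planning and delivery; technique feasible | start within 15 days, 3 of 5 |
| 2.2 and 11.0, secondary endpoint 3 | compliance with delivery | none; descriptive |
| 6.8 | limits on treatment breaks; dose compliance | not linked to the rule |
| Appendix II | A to E order, checked at each fraction | not linked to the rule |

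Every delivery requirement after the first fraction lies outside the rule.

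**3. What a positive result shows, under each reading of the start.**
- *Start of TFRT.* Five subplans and a composite plan were generated and assessed (6.6.1, 6.6.2), QA was done for each subplan as 6.6.3 expects, and one fraction was given. At that moment at most 1 of 5 subplans has been used.
- *Start of any radiation.* A patient switched to the fallback IMRT plan and started by day 15 also meets the criterion. The result then need not show a single TFRT fraction.

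**4. Sensitivity of the rule to delivery.** Let s be the probability of an on-time start, and d the probability that a patient who starts then receives the TFRT course as planned. Take patients as independent and 3/5 as at least 3. Values of s and d are illustrative assumptions; the documents give none.

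For a patient-level success probability p,

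P(X ≥ 3) = 10p³(1−p)² + 5p⁴(1−p) + p⁵.

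Under the rule as written p = s, and d does not appear. At s = 0.9: 10 × 0.729 × 0.01 + 5 × 0.6561 × 0.1 + 0.59049 = 0.0729 + 0.3281 + 0.5905 = 0.99. The same formula gives 0.94 at s = 0.8 and 0.68 at s = 0.6.

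For comparison only, a rule that also required delivery as planned would have p = s × d. At s = 0.9 and d = 0.6, p = 0.54 and P = 0.3332 + 0.1956 + 0.0459 = 0.57.

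| d | Rule as written, s = 0.9 | With delivery, s = 0.9 | Rule as written, s = 0.8 | With delivery, s = 0.8 |
|---|---|---|---|---|
| 1.0 | 0.99 | 0.99 | 0.94 | 0.94 |
| 0.8 | 0.99 | 0.86 | 0.94 | 0.75 |
| 0.6 | 0.99 | 0.57 | 0.94 | 0.46 |
| 0.4 | 0.99 | 0.25 | 0.94 | 0.19 |
| 0.2 | 0.99 | 0.04 | 0.94 | 0.03 |
| 0 | 0.99 | 0 | 0.94 | 0 |

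The two columns for the rule as written are constant for any choice of s. That follows from the form of the rule, not from the assumed values.

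**The case against.** The strongest reply is that the definition is disclosed. Wherever the objective appears as a definition of feasibility, the 15-day start is stated, so a careful reader knows what the result measures. For five patients, testing the extra planning and QA work against the clock is a reasonable primary question, and no hypothesis test or confirmatory claim depends on the label. All of this stands. It supports the start date as an endpoint, but it does not make a start date a measure of delivery, and it leaves the delivery wording in 3.1 with no criterion.

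Three stronger readings are tempting, and the documents do not support them.
- *A reader might infer that a positive result says nothing at all about delivery.* If the start means starting TFRT, it shows planning, QA and a first fraction.
- *A reader might infer that subplans could be given out of order unchecked, or that failed delivery would stay hidden.* Appendix II requires two therapists, confirmation of the previous fraction in Mosaiq, a fixed order, and a physicist present for any override. Section 6.8 requires treatment breaks and their reasons to be recorded, and compliance with delivery is a named secondary endpoint. The gap is in the primary claim and its rule.
- *A reader might treat one fraction out of 35, or three patients who start and none who finish, as the size of an error.* The first is not an error probability. The second is a logical extreme, and nothing in the documents indicates how likely it is.

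It is also fair to say that non-completion is not the same as delivery failure. Several reasons for removal in 6.11, such as progression, intercurrent illness or withdrawal, need have nothing to do with whether TFRT can be delivered.

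**Conclusion.** The point holds in limited form. Followed exactly, the plan can declare feasibility of planning and delivery on evidence that ends at the first fraction, and on a literal reading on evidence that includes IMRT starts. The probability of a positive declaration depends only on the on-time start rate (0.68, 0.94 and 0.99 at assumed rates of 0.6, 0.8 and 0.9) and not on what happens afterwards. Those probabilities rest on illustrative start rates, independence between patients and reading 3/5 as at least 3. The finding that delivery has no influence on the decision rests on none of these.

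This is a conclusion wider than the design supports. It is not a flaw in the choice of a timing endpoint, and it is not evidence that delivery would fail. It should be corrected because it bears on the headline claim and the correction is cheap.

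**What to change.** 1. In 2.1, 11.0 and the summary, restate the primary objective and the conclusion as feasibility of TFRT planning and on-time start of the TFRT plan. Name the TFRT plan in the criterion, so that a start on the fallback IMRT plan is not counted as a success. Align 3.1. The 3/5 rule can stay as it is for this narrower claim.
2. Define secondary endpoint 3 as the number of the 35 fractions, per patient, delivered with the assigned TFRT subplan in sequence. A patient who starts on IMRT scores 0 of 35. State how fractions after an adaptive replan (6.5.3) are classified.
3. Record the reason for each shortfall, separating TFRT-related reasons from progression, illness or withdrawal.
4. Report this listing for all patients beside the primary result, and base any statement about feasibility of delivery on it. If the team wants a formal delivery criterion inside the rule, it must set the definition and threshold in advance; the narrower claim does not need one.

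Cost: a narrower headline claim, wording changes in four places and a short table. Appendix II already has each previous fraction confirmed in Mosaiq, so the source records should exist. The study calendar and endpoint 3 do not specify this count, so its extraction has to be written in. No patients or visits are added, and treatment does not change.
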